At One Hope, participants will be identified in three ways: 1) New patients who call the clinic and indicate that they need to see a provider specifically about diabetes will be told about the study using an approved script, 2) Every patient seen at the clinic has an exit interview (*salida*) conducted by a Community Health Worker. For patients who have been told by their provider to have their A1c checked or that they have a diagnosis of diabetes or prediabetes, they will be told about the study using an approved script, and 3) Flyers about the study will be posted in the One Hope waiting room. For those who indicate interest in participating, a PDCS will contact them, inform them about the research per IRB requirements, and screen them for eligibility. For those who are eligible, the PDCS will schedule an appointment to consent them and gather baseline data.

PROTOCOL TITLE: Comparing Program Options for Latinos with Diabetes

At both sites, interested patients who qualify will provide contact information for a person that they identify from their social network (family or friend) whom they consider as their primary “social support.” A member of the research team will contact the social support, provide them with information about the study, and invite them to participate. The PDCS will schedule an appointment with supports who are interested.

At the appointment, the PDCS will ask all participants to sign the consent, collect the information in the Participant Data Sheet, and collect responses to the baseline survey questions. The PDCS will also obtain a blood sample, measure BMI, and gather a hair sample for the patient only.

Subset of Patient and Social support Participants for Interviews (72) and Focus Groups (72): At each of the sites, the PDCS will identify a convenience sample of interviewees and focus group participants from those already recruited to be in the study and invite them to participate. Our Research Manager will contact those interested to schedule.

3.2 *Describe the criteria that define who will be included or excluded in your final study sample.*

Staff & Providers will be individuals who work at one of the two sites.

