Eligibility Screening: potential participants who agree to being screened for eligibility will be contacted by a member of the research team and asked the eligibility screening questions, including requesting information about a potential social support partner. The patient participant will be offered the opportunity to contact their potential social support partner to inform him or her that a research team member will be in contact to conduct an eligibility screening. When the patient partner gives permission to contact the potential social support partner, a member of the research team will contact the potential social support partner and conduct the eligibility screening. If both the patient participant and his or her social support partner are deemed eligible, baseline data collection appointments will be scheduled with both participants. The information collected during the eligibility screening will be hand-written on an Eligibility Screening form and given to the Patient Engagement Coordinator, who will enter it into REDCap in the Eligibility Screening project. The Patient Engagement Coordinator will then create a record for the participant in the PCORI Diabetes Project in REDCap and assign a participant ID (PID) to the participant. The Patient Engagement Coordinator will keep a master list of the participants' names and PIDs both electronically and in hard copy. The electronic copy will be saved on her password-protected laptop, which is stored in a locked cabinet at One Hope when not in use. The hard copy will also be stored in a locked cabinet at One Hope.

Data Collection: at the baseline data collection appointment, the PDCS will collect and enter contact and demographic information into separate data collection instruments in the PCORI Diabetes Project in REDCap. At the baseline and all three follow-up appointments, the PDCSs will also administer the survey instrument to the participants, responses to which will be entered into a third data collection instrument in the same project. The PDCSs will also collect BMI measurements (weight and height) and draw blood for A1c testing at the baseline and all follow-up appointments and will collect a hair sample at the baseline and six-month follow-up appointment. The BMI measurements will be entered into a fourth data collection instrument in the PCORI Diabetes Project by the PDCS during

PROTOCOL TITLE: Comparing Program Options for Latinos with Diabetes

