A1c: The PDCSs will be trained in phlebotomy. The PDCS will draw blood samples at the same time they administer the survey. The UNM Clinical and Translational Science Center (CTSC) Clinical Research Laboratory will provide the collection kits for specimen collection. Blood will be drawn, labeled and stored using standard phlebotomy protocols, and the *Patient Engagement Coordinator* will deliver specimens to the CTSC lab where they will be tested on whole blood following the lab's "*Hemoglobin A1c*" procedure using the DCA Vantage 2000 analyzer⁹¹. After testing, specimens will be disposed of according to CTSC lab protocol. For A1c (>10), we will notify the participant's PCP. If we see a lab value that could indicate an emergency (Glucose > 400 mg/dl, < 60 mg/dl), we will contact the participant to make sure they are aware of their A1c status and that they are receiving appropriate care. For women with an elevated A1c, when we contact them to tell them about their elevated test results we will inquire again whether or not they are or think they might be pregnant. If so, Co-Investigator [name] will provide them with a referral to UNM's High Risk Obstetrics Clinic. Additionally, we have discovered that there is a difference between the A1c test that CTSC runs and the test run at Quest or TriCore. The test CTSC uses is reliably .2 lower and this is cited in the literature. Therefore, it is appropriate for us to enroll individuals who have a test at another lab that shows them to be pre-diabetic (A1c 5.7-6.4) even if our baseline lab comes back lower (5.5-6.2). However, any individual whose blood gathered by our data collectors at baseline returns with an A1c below 5.5 will be disenrolled.

Body Mass Index (BMI): The PDCS will document patient participant height and weight and calculate his or her BMI. Height and weight measurements will be taken using a standardized protocol. Height measurements will be collected using SHORR boards against

PROTOCOL TITLE: Comparing Program Options for Latinos with Diabetes

flat walls on level, firm (not carpeted) flooring. Weight measurements will be collected using calibrated, research-grade SECO scales. Two measurements will be taken for height and two for weight for each participant at each data collection point. An average of the two measures of height and an average of the two measures of weight will be used in the BMI calculation.

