1.) **A1c:** For patients from CDE-UNMH, we will obtain baseline A1c results from the CDE program files. For One Hope patients, the PDCS who will be trained in phlebotomy will draw blood samples at the same time they administer the baseline survey. For patients from both sites, the PDS will draw blood samples at the 3-month, 6-month and 12-month data collection sessions. Blood will be drawn, labeled and stored using standard phlebotomy protocols, and the *Patient Engagement Coordinator* will deliver specimens to the CTSC lab where they will be tested for A1c.

2.) **Body Mass Index (BMI):** The PDCS will document patient height and weight and calculate his or her BMI. Height and weight

PROTOCOL TITLE: Comparing Program Options for Latinos with Diabetes

measurements for all participants will be taken using a standardized protocol. Height measurements will be collected using SHORR boards against flat walls on level, firm (not carpeted) flooring. Weight measurements will be collected using calibrated, research-grade SECO scales. Two measurements will be taken for height and two for weight for each participant at each data collection point. An average of the two measures of height and an average of the two measures of weight will be used in the BMI calculation.

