At One Hope, participants will be identified in three ways: 1) New patients who call the clinic and indicate that they need to see a provider specifically about diabetes will be told about the study using an approved script, 2) Every patient seen at the clinic has an exit interview (*salida*) conducted by a Community Health Worker. For patients who have been told by their provider to have their A1c checked or that they have a diagnosis of diabetes or prediabete, they will be told about the study using an approved script, and 3) Flyers about the study will be posted in the One Hope waiting room. For those who indicate interest in participating, a PDCS will contact them, inform them about the research per IRB requirements, and screen them for eligibility. For those who are eligible, the PDCS will schedule an appointment to consent them and gather baseline data.

At both sites, interested patients who qualify will provide contact information for a person that they identify from their social network (family or friend) whom they consider as their primary "social support." A member of the research team will contact the social support, provide them with information about the study, and invite them to participate. The PDCS will schedule an appointment with supports who are interested.

At the appointment, the PDCS will ask all participants to sign the consent, collect the information in the Participant Data Sheet, and collect responses to the baseline survey questions. The PDCS will obtain a blood sample and measure BMI for the patient only.

Subset of Patient and Social support Participants for Interviews (72) and Focus Groups (72): At each of the sites, per our sampling frame described above, the PDCS will identify interviewees and focus group participants from those already recruited to be in the study and invite them to

PROTOCOL TITLE: Comparing Program Options for Latinos with Diabetes

participate. Our Research Manager will contact those interested to schedule.

23.2 Describe the source of subjects.

We will recruit patients from two sites: The Center for Diabetes Education at UNMH and One Hope Clinic. Patients will identify a corresponding social support participant to be invited. We will also identify site staff and provides to participate in interviews.

23.3 Describe the methods that will be used to identify potential subjects.

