At the appointment, the PDCS will ask all participants to sign the consent, collect the information in the Participant Data Sheet, and collect responses to the baseline survey questions. The PDCS will also obtain a blood sample, measure BMI and gather a hair sample for the patient only.

Subset of Patient and Social support Participants for Interviews (72) and Focus Groups (72): At each of the sites, per our sampling frame described above, the PDCS will identify interviewees and focus group participants from those already recruited to be in the study and invite them to participate. Our Research Manager will contact those interested to schedule.

The seven patient members of our Patient Advisory Board will be invited to participate in the Advisory Board Member interviews.

23.4 Describe materials that will be used to recruit subjects. (Attach copies of these documents with the application. For advertisements, attach the final copy of printed advertisements. When advertisements are taped for broadcast, attach the final audio/video tape. You may submit the wording of the advertisement prior to taping to preclude re-taping because of inappropriate wording, provided the IRB reviews the final audio/video tape.)

At CDE-UNMH, when patients register for the program, CDE-UNMH staff will tell them about the study using an IRB-approved script and a flyer with pull-off tabs will be posted in the CDE office. An invitation with further detail about the research and contact information for our PDCSs--the *Patient Data Collection Specialists* (PDCSs)--will be sent in a mailing that all new patients receive from CDE-UNMH with their class schedule confirmation and logistics. A staff person at CDE-UNMH or a member of the research team will phone new participants to tell them about the study. For those who indicate that they are interested, the staff person or research team member will ask the patient's permission to release their name and contact information to our research team. If the patient agrees, a member of the research team will contact the patient. Interested patients can also contact the research team using the information on the mailing. For all interested patient participants, the research team will screen them per our recruitment criteria.

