At One Hope, participants will be identified in three ways: 1) New patients who call the clinic and indicate that they need to see a provider specifically about diabetes will be told about the study using an approved script, 2) Every patient seen at the clinic has an exit interview (*salida*)

PROTOCOL TITLE: Comparing Program Options for Latinos with Diabetes

conducted by a Community Health Worker. For patients who have been told by their provider to have their A1c checked or that they have a diagnosis of diabetes or prediabetes, they will be told about the study using an approved script, and 3) Flyers about the study will be posted in the One Hope waiting room. For those who indicate interest in participating, a PDCS will contact them, inform them about the research per IRB requirements, and screen them for eligibility. For those who are eligible, the PDCS will schedule an appointment to consent them and gather baseline data.

At both sites, interested patients who qualify will provide contact information for a person that they identify from their social network (family or friend) whom they consider as their primary “social support.” A member of the research team will contact the social support, provide them with information about the study, and invite them to participate. A member of the research team will schedule an appointment with supports who are interested.

At the appointment, the PDCS will ask all participants to sign the consent, collect the information in the Participant Data Sheet, and collect responses to the baseline survey questions. The PDCS will also obtain hair and blood samples, and measure BMI for the patient only.

Subset of Patient and Social support Participants for Interviews (72) and Focus Groups (72): At each of the sites, per our sampling frame described above, the PDCS will identify interviewees and focus group participants from those already recruited to be in the study and invite them to participate. Our Research Manager will contact those interested to schedule.

For staff and provider interviews, the Research Manager will obtain names from our site liaison and will invite them using an approved script.

For Patient Advisory Board interviews, we already have names and contact information for the seven patient members of our Patient Advisory Board. We will invite them to participate using an approved script.

23.5 *Describe the amount and timing of any payments to subjects.*

Research Appointments

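### The source of baseline A1c at CDE-UNMH is contradictory; taking it from program files would tie any laboratory or timing difference to site in the A1c secondary endpoint

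*Combined protocol and SAP*

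**What the plan says.** Section 11.5, item 1(v), Physical Measures, treats the two sites differently at baseline. For one site it says "For patients from CDE-UNMH, we will obtain baseline A1c results from the CDE program files". One Hope patients have blood drawn by the study's data collectors at the baseline survey. The sentence covering both sites starts only at follow-up: "For patients from both sites, the PDS will draw blood samples at the 3-month, 6-month and 12-month data collection sessions".

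Other current sections plan a baseline study draw with no exception for CDE-UNMH:

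- Section 9.2 (Data Collection), repeated in section 25.3: data collectors "draw blood for A1c testing at the baseline and all follow-up appointments".
- Section 9.2 (Physical Measures, A1c): "The PDCS will draw blood samples at the same time they administer the survey". The survey is given at baseline, and the specimens go to the CTSC laboratory.
- Section 3.1, on the baseline appointment, directly after text covering both sites: "The PDCS will also obtain a blood sample, measure BMI, and gather a hair sample for the patient only".
- Sections 23.1, 23.3 and 23.4, on the same appointment: "The PDCS will obtain a blood sample and measure BMI for the patient only", "The PDCS will also obtain a blood sample, measure BMI and gather a hair sample for the patient only" and "The PDCS will also obtain hair and blood samples, and measure BMI for the patient only".

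The rule that disenrols anyone whose baseline study blood shows A1c below 5.5 (sections 3.2, 8.1 and 9.2) also assumes a baseline study draw. It compares a qualifying test from an outside laboratory with the study's own baseline result, and it is not limited to one site. The same text says that CTSC reads 0.2 lower than Quest or TriCore.

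The A1c secondary endpoint is change from baseline to 6 months, compared by site in a mixed model (sections 11.1 and 11.2). No laboratory term is named.

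**The concern.** A change score is comparable between sites only if both ends of it are measured in the same way at each site. Under section 11.5, One Hope would have one laboratory at both ends. CDE-UNMH would have a file value from an unnamed laboratory, on an unstated date, followed by a CTSC result.

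Any difference between the file laboratory and CTSC, and any effect of the age of the file value, would then coincide exactly with site. It would enter the site-by-time contrast, which is the estimate of interest. Covariates and propensity strata could not separate it from the program effect, and a larger sample would not reduce it. If the file values came from Quest or TriCore, the DSMS program would be credited with a fall in A1c that did not occur.

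The below-5.5 check is written for blood taken by study staff. Under section 11.5 it could operate at baseline only at One Hope, so eligibility would also differ by site.

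**Working it through.** **Inputs.** From section 11.2: 96 analysed per site, SD of change 1.0, CCM minus DSMS difference -0.5, alpha 0.017, stated power 84%. From sections 3.2, 8.1 and 9.2: CTSC reads 0.2 below Quest or TriCore. Two-sided testing is stated for the primary comparisons and assumed here. A two-sample t test stands in for the planned mixed model.

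**Reproducing the plan's power.**

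- SE = 1.0 × √(2/96) = 0.1443; df = 96 + 96 − 2 = 190; critical t = 2.408
- Noncentrality = 0.5 / 0.1443 = 3.464, giving power 0.853
- Treating the stated effect size of 0.06 as f² gives 0.837

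Both agree with the stated 84%, so the plan's figure is not in dispute.

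**Effect of mixing sources.** Let *s* be the share of CDE-UNMH file values that come from Quest or TriCore, with the rest assumed to be CTSC assays.

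- One Hope: CTSC at 6 months minus CTSC at baseline, shift 0
- CDE-UNMH: CTSC at 6 months minus (CTSC-equivalent baseline + 0.2*s*), shift −0.2*s*
- CCM minus DSMS: shift +0.2*s*, so the planned −0.5 is seen as −0.5 + 0.2*s*

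Power uses noncentrality (0.5 − 0.2*s*)/0.1443. With no true difference, rejection in favour of DSMS uses noncentrality 0.2*s*/0.1443. Coverage of the 98.3% interval (half-width 2.408 × 0.1443 = 0.348) is 1 minus both rejection tails.

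| Share *s* | Shift | Apparent difference | Power | False result for DSMS | Coverage |
|---|---|---|---|---|---|
| 0% | 0 | −0.50 | 0.853 | 0.0085 | 0.983 |
| 25% | 0.05 | −0.45 | 0.760 | 0.0205 | 0.976 |
| 50% | 0.10 | −0.40 | 0.642 | 0.0447 | 0.954 |
| 75% | 0.15 | −0.35 | 0.508 | 0.0877 | 0.912 |
| 100% | 0.20 | −0.30 | 0.373 | 0.1559 | 0.844 |

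The full shift is 0.2/0.5 = 40% of the planned difference. The table covers the assay difference only. The age of the file values, and any laboratory other than these three, are not modelled.

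**The case against.** The strongest reply is that the section 11.5 sentence is leftover text and would not be followed. Section 11.1 describes A1c as measured from drawn blood at all four visits. Elsewhere A1c results enter the database only when a laboratory sends them, and the lists of source records and of data collected name no form for extracting A1c from CDE files. The supporting statements are also less independent than their number suggests: the sentences in 9.2 and 25.3 are the same, and those in 3.1, 23.1, 23.3 and 23.4 are near copies.

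Much of this is fair, and the sentence may well be unrevised. But it is in the current protocol, in the section on study-wide handling of data and specimens, and it is the only text that deals specifically with CDE-UNMH baseline A1c. Staff could reasonably let the specific instruction override the general one. The section 11.1 wording is too loose to settle the matter, since it also lists hair cortisol at all four visits although hair is taken only at baseline and 6 months.

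Three further points stand as limits:

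- No document says that CDE files hold Quest or TriCore results, so applying the 0.2 to them is an assumption.
- A known, constant assay offset could be corrected by calibration if the laboratory were recorded. An unrecorded laboratory, or an old value, could not be corrected in this way.
- If every CDE-UNMH baseline were a file value, a sensitivity analysis excluding file values would leave no DSMS baseline. It is useful only as a contingency once the study draw is the rule.

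**Conclusion.** The contradiction is certain: section 11.5 and the baseline-draw sections cannot both determine the CDE-UNMH baseline value. The harm is conditional. It arises only if section 11.5 is followed, and it is confined to A1c, one of three secondary outcomes; DKQ and PAM-13 are untouched.

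Using the protocol's own assay difference, the shift in the site contrast runs from 0 (file values are CTSC assays, or the study draw governs) to 0.2 (all are from Quest or TriCore), with the consequences tabulated above. These are illustrations, not bounds: another laboratory or older values could move the result by an amount, or in a direction, that the documents do not allow us to state. This should be fixed, with medium confidence that it would affect the result in practice.

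**What to change.** 1. Amend section 11.5 to agree with sections 3.1, 9.2, 23.1, 23.3, 23.4 and 25.3, so that one baseline source and one laboratory serve both sites and supply the baseline for the A1c analysis. Extending the both-sites sentence ("For patients from both sites, the PDS will draw blood samples at the 3-month, 6-month and 12-month data collection sessions") to the baseline session, with testing at CTSC, would do this.
2. Reconcile section 11.5 with the below-5.5 text in sections 3.2, 8.1 and 9.2, so that the baseline A1c eligibility check operates in the same way at both sites.
3. Record the laboratory and test date of any baseline value that still has to come from files, and specify now a sensitivity analysis of the A1c endpoint that excludes such values.

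The cost is a wording change in section 11.5 and one sentence for the sensitivity analysis. The baseline draw is already planned, so no new procedure is added. It should be settled before enrolment, because a missed CDE-UNMH baseline draw cannot be recovered later.
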